## 13.7 Mechanistic Evaluation

The mechanistic evaluation will be conducted through a structural equation modelling approach that is particularly well suited to estimating causal relationships using a combination of quantitative data and qualitative causal assumptions . DNA fragmentation will be measured though the comet assay and through slide-based acridine orange assay and summarised through the latent variable DNAfrag (Fig 6). Similarly, chromatin compaction measured by aniline blue and CMA3 assays will be summarised through the latent variable Chrom. HALO provides a separate covariate of sperm nuclear integrity. These two latent variables (DNAfrag, Chrom), and HALO are covariates in a regression model for Hyaluronan Binding Score (HBS) which in turn is a covariate for the logistic regressions for each of the clinical outcomes

(biochemical pregnancy at two weeks, clinical pregnancy at 6–8 weeks, miscarriage rate, and live birth at  $\geq$ 37 weeks. The structural equation modelling can be undertaken with the software MPLUS version 6.12.

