### 11.9 Selection of Samples for Laboratory Mechanistic Assessments

The Birmingham Mechanistic Laboratory will thaw out single aliquots and cytology will be performed on all or as many of the 3730 trial samples as possible. Cytology provides an important primary benchmark on the integrity of the semen samples

The mechanistic evaluations will be performed following PCTU stratification of the clinical HBS values (three scoring strata: <50%, 50-65%, >65%, HBS). The routine cytology will then determine if there is sufficient sample available; it is anticipated that a significant proportion of the samples will have insufficient sperm for further mechanistic evaluation. However, the stratification will generate a balanced sampling framework from each trial arm across the three HBS strata. Those samples identified by PCTU from their HBS for the mechanistic evaluation will be communicated to the HBRC central sample repository. The HBRC will then coordinate sample transfer to the four mechanistic laboratories to perform the hierarchy of mechanistic test evaluations as described in Figure 5 and Table 3.

In summary, the PCTU will select the HABSelect semen samples to be used for mechanistic analysis based on HBS and communicate this to the HBRC who will arrange shipment to the appropriate Mechanistic Laboratories. This process can be reiterated until ~900\* samples have been tested with each assay across the three, <50% 50-65%, >65%, HBS strata. It is anticipated that access to screening the full complement of 3730 trial samples in order to achieve this may be required. With dynamic PCTU and Birmingham monitoring of sample selection for analysis, it will be possible to obtain high quality information for each test in each stratum even if only a minority of samples is amenable to global examination by *all* tests. Local statistical support is confident that the information can be integrated. Shipment of samples to the mechanistic labs will follow the same operating procedures as transport of the samples from the participating centres to the central storage bank.

\* Belfast will take 450 samples for analysis but will analyse them using two distinct variations of the comet assay.

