#### 11.9.1 Mechanistic assessments

Four basic science laboratories will perform mechanistic evaluation of the collected semen samples according to the following order:

- Birmingham cytology, TUNEL, Acridine Orange (AO) stain
- Belfast -Comet

\*

- Sheffield HALO, Aniline Blue
- Leeds -TUNEL, HALO, Aniline Blue, CMA3
- semen sampling >> DDG centrifugation 40:80 **PVP-ICSI** PICSI frozen storage 2.Cytology < remaining pellet (interface) (Birm) frozen storage 🚽 (pellet) 1.HBA scoring (HBS) 3a.Comet 3b.TNL **4**.AO 5.HALO 6a.CMA3 6b.AB <50% 50-65% >65% (Belfast) (Birm/Lds) (Birm) Lds/Sheff (Lds) Lds/Sheff Sample selection < Online database

**Figure 5**. Schematic of mechanistic protocol. There is a hierarchical priority of testing, with the number carried out depending on the number (Table 2, **N**) of available sample aliquots after HBA scoring. The testing priority is 1, 2, 3a AND/OR 3b, 4, 5, 6a AND/OR 6b. If four aliquots are available, all tests can be carried out across the four centres. If three aliquots are available, going to three centres, it will not be possible to replicate tests 5 and 6 in both Lds and Sheff. If two aliquots are available, going to two centres the same restrictions will apply and additionally, only one of tests 4, 5 or 6 will be possible. All samples will be stored centrally in Birmingham HBRC; hence they can begin to process and assess samples for distribution as soon as they are ready. If following cytology (1), there is only sufficient sample for analysis at one centre, it will be Birm who carries out any additional tests. PCTU will assist in maximising the use of available samples by all mechanistic labs. Collection of sperm from the 40:80 interface will occasionally be undertaken on CI request for the mechanistic studies.

**Table 3.** Mechanistic assays are subject to a hierarchical order of importance as follows: 1.  $HBS^{CL} > 2$ .  $Cytology^{BI} > 3$ .  $(aComet^{BL} = bTunel^{BI}) > 4$ . AO stainBI > 5.  $HALO^{SH, LE} > 6$ . (aAniline BlueSH, LE = bCMA3SH, LE). It is assumed that the HBS (1) will be carried out on all samples by the clinics prior to aliquoting.

Equivalent available	Test
aliquots (N)‡	
4	2, 3a, 3b, 4, 5, 6a, 6b
3	2, 3a, 3b, 4, 5*, 6*
2	2, 3a, 3b, 4 OR 5* OR 6*
1	2, 3b, 4

CL, clinical labs; BI, Birmingham; BL, Belfast; LE, Leeds; SH, Sheffield.

\* Sent to either of the two centres carrying out these assays. To balance the numbers, tests

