#### 13.5 Sample size - Mechanistic evaluation

The sample size for the clinical trial (3,730) is based on detecting a 5% improvement in live birth outcome at 90% power (3,266). In contrast, the mechanistic sample size is based on an estimated minimum of 180 required for logistic regression analysis of the relationship between HBS and clinical outcomes  and can therefore be far smaller. While this number accommodates the potentially limiting availability of samples with low (<50%) HB scores (estimated at ~10% or ~370), it is a minimum estimate that does not satisfy the need to more accurately specify the relationships between the mechanistic and clinical outputs of this study that are less dependent on HB scoring (such as sperm concentration). Furthermore, as indicated elsewhere, many of the samples will not be amenable to mechanistic tests. Hence, the chosen mechanistic sample size is a balance between minimum sample size requirements (180) required to link clinical and mechanistic outcomes, the need to access more samples in order to accommodate limitations in their use and the relative cost of analysis. Assuming that  $\sim$ 20% of samples can be examined by one or more tests based on cytology, only 36/180 will satisfy the criteria. Hence ~900 samples (180/36\*180) are required overall. All mechanistic tests are needed to facilitate the identification of the form of damage that compromises sperm function in relation to clinical outcome (Fig 6).

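### Section 13.7 gives TUNEL no stated role in the DNA fragmentation factor, although Table 3 ranks it equal to comet and runs it in every aliquot row

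*Protocol*

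**What the plan says.** **The model.** Section 13.7 states: "DNA fragmentation will be measured though the comet assay and through slide-based acridine orange assay". These two assays are summarised as DNAfrag. Aniline blue and CMA3 form Chrom, and HALO enters as a separate covariate. All three are regressors for HBS, which in turn predicts the clinical outcomes. TUNEL does not appear in this text.

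**The assay plan.** Section 11.9.1 lists Birmingham for "cytology, TUNEL, Acridine Orange (AO) stain", with TUNEL also at Leeds. Figure 5 gives the order: "The testing priority is 1, 2, 3a AND/OR 3b, 4, 5, 6a AND/OR 6b", where 3a is comet, 3b TUNEL and 4 acridine orange. Table 3 sets 3a and 3b equal. Its row for one equivalent aliquot gives cytology, TUNEL and acridine orange, without comet. Its row for two reads "2, 3a, 3b, 4 OR 5* OR 6". Its rows for three and four give all three assays.

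**The numbers.** Section 11.9 sets a target per assay: "This process can be reiterated until ~900". Its footnote limits comet: "Belfast will take 450 samples for analysis but will analyse them using two distinct variations of the comet assay". Section 13.5 adds that every mechanistic test is needed to identify the form of damage.

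**The concern.** TUNEL is the only assay ranked 3 to 6 that has no place in the model text, and the protocol gives no reason. By Table 3 it is also the only one of the three DNA fragmentation assays that is run whatever the number of aliquots. The model keeps comet, which has the smaller sample target, and acridine orange, which can be dropped at two aliquots.

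This is not mere silence left for a statistical analysis plan. Section 13.7 names an indicator set, and that set does not match sections 11.9, 11.9.1 and 13.5. At stake is how well DNAfrag is measured, and so the precision of its path to HBS. That path bears on the primary mechanistic objective (section 6.1.1.2). The randomised comparison is not touched.

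**Working it through.** **1. The plan's own figure.** Section 13.5 starts from an "estimated minimum of 180 required for logistic regression analysis" and assumes that about 20% of samples can be tested: 180 / 0.20 = 180/36 × 180 = 900. This reproduces.

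**2. Share of samples with one DNAfrag indicator, from the section 11.9 targets.** Take acridine orange on 900 samples and comet on 450, with *v* samples having both. Samples with either assay = 900 + 450 − v. Samples with exactly one = 900 + 450 − 2v.

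| Overlap v | With either | With exactly one | Share |
|---|---|---|---|
| 450 | 900 | 450 | 50% |
| 225 | 1125 | 900 | 80% |
| 0 | 1350 | 1350 | 100% |

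Half is therefore the floor under these targets.

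**3. The same share from Table 3, ignoring the comet limit.** Let f1 and f2 be the shares of samples with one and two equivalent aliquots, and *a* the share of two-aliquot samples sent for acridine orange. One-indicator share = f1 + f2(1 − a). The protocol gives none of these values. With f1 = f2 = 1/3 and a = 1/3 (assumed), it is 1/3 + 1/3 × 2/3 = 56%. Over the other assumed splits tried, it runs from 10% (f1 = 0.1, f2 = 0.2, a = 1) to 80% (f1 = 0.6, f2 = 0.2, a = 0). In two-aliquot samples not sent for acridine orange, the single indicator is comet.

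**4. Indicators per Table 3 row, without and with TUNEL.**

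| Equivalent aliquots | Comet + acridine orange | Adding TUNEL |
|---|---|---|
| 1 | 1 (acridine orange) | 2 |
| 2 | 1 or 2 | 2 or 3 |
| 3 or 4 | 2 | 3 |

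Where Table 3 is followed, the one-indicator share falls to zero. Some such samples could remain if the and/or in Figure 5 is used to skip 3a or 3b, or once the comet limit is reached.

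**5. Reliability.** With k indicators of equal loading λ, composite reliability = kλ² / (1 + (k − 1)λ²). At λ = 0.6 it is 0.36, 0.53 and 0.63 for k = 1, 2 and 3.

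**6. Precision of the DNAfrag-to-HBS path.** The set-up is assumed: one normal factor, equal loadings, independent errors, 900 samples with acridine orange (and TUNEL where included), comet on 450 of them, and a standardised path of -0.3. The expected information is the sum over the two missing-data patterns, 450 × I(complete) + 450 × I(no comet). Each element of I is ½ tr(Σ⁻¹ ∂Σ/∂θi Σ⁻¹ ∂Σ/∂θj). The standard error comes from its inverse. The effective-sample ratio is the square of the ratio of standard errors.

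| Loading | SE without TUNEL | SE with TUNEL | Ratio of effective n |
|---|---|---|---|
| 0.5 | 0.062 | 0.048 | 1.7 |
| 0.6 | 0.051 | 0.041 | 1.5 |
| 0.7 | 0.044 | 0.037 | 1.4 |
| 0.8 | 0.038 | 0.034 | 1.25 |

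**The case against.** The strongest case on the other side has five parts.

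- **TUNEL may not be unused.** Section 13.7 refers to Figure 6, which cannot be seen here. Section 13.1.2.2 plans to model the chromatin and DNA integrity tests against live birth and miscarriage, and excludes none of them. This stands. A reader might infer that the plan discards TUNEL; the text supports only that 13.7 gives it no stated role. If Figure 6 does draw it, text and figure disagree and need reconciling.
- **The factor is not in trouble.** A reader might infer that two indicators, one often missing, leave DNAfrag unidentified or nearly so. That goes too far: HBS, Chrom and HALO help to identify it, and a full-information fit can keep one-indicator samples. The loss is one of precision.
- **Comet comes in two variants.** These could serve as two indicators. But they share a laboratory and the same 450 samples, and do nothing for samples without comet.
- **The half is inferred.** This stands. No count specific to TUNEL or acridine orange is given, and section 13.5 can be read as 900 samples drawn to yield 180 testable ones. The figure rests on section 11.9.
- **The calculation favours the fix.** It assumes that TUNEL loads as well as the others, is complete and has its own independent error. Birmingham runs both TUNEL and acridine orange, so shared laboratory error would shrink the gain. The note to Table 3 links equivalent aliquots to sperm count, so comet is not missing completely at random. Both points stand and shape the fix.

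**Conclusion.** The concern holds in a limited form. The indicator set stated in section 13.7 does not match the protocol's own assay priorities, and an equally ranked assay that is already planned has no stated place in the model.

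Under the section 11.9 targets, at least half of the samples would rest on one DNAfrag indicator, either acridine orange or comet. Including TUNEL is worth about 1.25 to 1.7 times the effective sample size for the DNAfrag-to-HBS path. This assumes equal loadings of 0.8 down to 0.5, independent errors and a path of -0.3, none of which the protocol gives. A small simulation of the same set-up can suggest a gain above two at loading 0.5; the expected information does not support that. The gain is smaller if TUNEL and acridine orange share laboratory error.

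Section 13.5 calls the mechanistic components exploratory, and the primary clinical analysis is unaffected. This is a worthwhile improvement, not a threat to the trial's main result.

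**What to change.** In section 13.7, and in Figure 6 if it omits TUNEL:

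1. Define DNAfrag by comet, TUNEL and acridine orange.
2. Fit the model by full-information maximum likelihood, so that samples without comet or without acridine orange still contribute.
3. Include sperm concentration as an auxiliary variable or covariate, because comet availability depends on sperm count.
4. Check a residual correlation between TUNEL and acridine orange where both are run in the same laboratory.

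If there is a subject-matter reason to keep TUNEL out of the factor, state it and say how TUNEL will be used.

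The cost is a short edit to 13.7, the figure and the analysis plan, and a slightly more complex model. No new samples or assays are needed.

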### **5.3.2** Evidence of the beneficial effect of HA selection on pregnancy outcome.

In many clinics, polyvinylpyrrolidone (PVP) is normally used to slow sperm down sufficiently for capture by the clinical embryologist. Two clinically relevant studies have reported on effects following a HA-selection procedure for ICSI. Parmegiani et al  obtained higher numbers of Grade 1 embryos for transfer following ICSI with HA rather than PVP-selected sperm (36% versus 24%) and an improved LBR (23% vs 18%). A more recent and larger randomised study used a fully developed HA based sperm selection (PICSI) versus PVP procedures in 802 ICSI cycles (Table 2 This study showed a 13% increase in CPR [N = 121]) using HA versus PVP selected sperm with a corresponding drop in miscarriage rate (14.1% vs 3.8%; N = 168). Closer examination of the trial data indicates a more general 5-10% improvement in CPR if the data are stratified according to the DGC washed HA binding score (obtained prior to PICSI selection), with lower scores (≤65%) giving the best results. This may explain why CPRs in HA versus PVP arms were balanced before stratification according to the post-DGC washed HA binding score, while pregnancy failure rates fell by 6% (Table 2). The US trial has now reported LBR, and provided strong supporting evidence for HA selection reducing early pregnancy failure . Our trial will seek to confirm this as well as contributing data on LBR, miscarriage rate and notably to a better understanding of the basic underlying mechanistic of action of HA sperm selection.

[figure not shown]
HBS	Implantation	CPR (%) at	MCR (%) based on C P with fetal
	rate (%) at 4	6-8 wks	sac (6 wks) less fetal heartbeat
	wks		(8 wks)
All scores	32.2 / 33.5 	47 .8/47.3 	10.0 / 4.3247
>65%	34.8 / 37.9	51.1/46.2 	7.8 / 5 .9 
≤65%	30.7 / 37.4	37.9/50.8 	18.5 / 0 

**Table 2**. Final output from the US clinical trial on PVP (blue) versus PICSI (green) based selection. Sample numbers are shown in superscript. HBS refers to the hyaluronan binding score for DGC washed sperm. From Worrilow et al, . Please see text for more details. Numbers in superscript indicate sample size.

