## 6.1.1.2 *Mechanistic:*

Evaluate if PICSI can compensate for poor sperm quality and investigate HBS in relation to chromatin integrity and LBR. Evaluate the differences in chromatin architecture in DGC washed and pelleted sperm with high and low HBS including any correlation with DNA damage.

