## 13.1.2.2 Mechanism:

Chromatin disruption in relation to DNA damage and DNA packaging anomalies in 45:90 interface samples and correlation between clinical and post-clinical HBA scores in relation to initial sperm concentration. The relationship between the tests of chromatin and DNA integrity with live birth outcome and miscarriage will be dynamically assessed by statistical modelling (please see section 13.7).

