In each case, an interaction test will first be used to determine whether there is a basis for investigating treatment efficacy within subgroups. Sub-group analyses results will be treated with caution, and will be undertaken in relation to the advanced analytical assays summarised in section 13.7 solely for the purposes of hypothesis generation.

As the two arms of this study are compatible with the equivalent arms of the US NIH trial (NCT00741494) they can be included in any future meta analysis of the data.

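### As described in section 13.7, the structural equation model names no randomised arm or arm-by-HBS term, so it cannot answer whether PICSI compensates for poor sperm quality

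*Protocol*

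**What the plan says.** Protocol section 6.1.1.2 opens the primary mechanistic objective with: "Evaluate if PICSI can compensate for poor sperm quality and investigate HBS in relation to chromatin integrity and LBR". The analysis is in section 13.7: "The mechanistic evaluation will be conducted through a structural equation modelling approach". That section then sets out the paths. Two latent variables, DNAfrag and Chrom, together with HALO, are covariates for HBS. HBS is in turn a "Hyaluronan Binding Score (HBS) which in turn is a covariate for the logistic regressions for each of the clinical outcomes".

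On measurement, section 13.7 states that "DNA fragmentation will be measured though the comet assay and through slide-based acridine orange assay". TUNEL does not appear there.

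Other relevant places:
- Sections 10.1 and 10.4: HBS is obtained on the prepared sample in both arms.
- Sections 11.9 and 13.5: the mechanistic samples are drawn in balance from each arm across three HBS strata.
- Section 13.1.2.2: "The relationship between the tests of chromatin and DNA integrity with live birth outcome and miscarriage will be dynamically assessed", with a cross-reference to section 13.7.
- Section 13.6.1: subgroup interaction tests include HBS split at 65% and sperm concentration split at 15. They are "solely for the purposes of hypothesis generation".
- Section 5.3.2: the earlier US trial is cited for stratified results "with lower scores (≤65%) giving the best results".

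**The concern.** Compensation means that the penalty for poor sperm quality is smaller under PICSI than under PVP. Statistically, the HBS-outcome slope differs between arms. A model without arm estimates one slope averaged over two arms, and nothing in it distinguishes a trial in which PICSI removes the penalty from one in which PICSI does nothing.

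HBS cannot stand in for allocation, because it is taken on the prepared sample in both arms and so acts as a potential effect modifier. Arm has to enter as a term of its own. The samples are balanced by arm, so it could.

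Two smaller gaps sit in the same paragraph. Section 13.1.2.2 looks to section 13.7 for the relation of the assays to live birth and miscarriage, but the described paths reach the outcomes only through HBS. And TUNEL, which the protocol ranks level with Comet, is not among the indicators of DNAfrag.

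At stake is whether the trial can report on its first mechanistic objective with a planned analysis, or only with an exploratory subgroup result.

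**Working it through.** **1. Objective against model.**

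| Question in the objectives | Term needed | Named in 13.7? |
|---|---|---|
| Does PICSI compensate for poor quality (6.1.1.2)? | arm × HBS on outcome | No |
| HBS and chromatin integrity (6.1.1.2) | DNAfrag, Chrom, HALO → HBS | Yes |
| HBS and live birth (6.1.1.2) | HBS → outcome | Yes |
| Assays and live birth, miscarriage (13.1.2.2) | assays → outcome | Only through HBS |

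The caption of Figure 6 mentions only DNAfrag and Chrom as covariates for HBS.

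**2. Can the described model tell compensation from no effect?** Assumed live birth rates, 1:1 allocation, HBS low or high, logit(p) = ln[p/(1−p)]:
- World A, PICSI has no effect: low HBS 24%, high HBS 29%, in both arms.
- World B, full compensation: low HBS 19% on PVP and 29% on PICSI; high HBS 29% in both.

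Without arm, the low-HBS rate in B is (19% + 29%)/2 = 24%, the same as in A. The slope, low against high, is logit(0.24) − logit(0.29) = −0.26 in both worlds.

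With arm, the interaction is 0 in A. In B it is [logit(0.29) − logit(0.29)] − [logit(0.19) − logit(0.29)] = 0 + 0.55 = 0.55.

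**3. The protocol's own motivating data.** Table 2, clinical pregnancy, HBS >65% against ≤65%:
- PVP: (0.511/0.489)/(0.379/0.621) = 1.71
- PICSI: (0.462/0.538)/(0.508/0.492) = 0.83
- Averaged over equal arms, 48.65% against 44.35%: (0.4865/0.5135)/(0.4435/0.5565) = 1.19

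Table 2 gives no split by arm. Assuming equal arms within 357 high-HBS and 121 low-HBS couples, the 95% intervals are 0.94 to 3.11 (PVP) and 0.46 to 1.49 (PICSI). The ratio of the two odds ratios has p of about 0.09. The direction illustrates the point; it does not establish it.

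**4. Precision of the missing term.** The mechanistic size is reproduced: 180/36 × 180 = 900. Section 13.5 bases its minimum of 180 on HBS against outcome, not on an interaction. Power for World B's interaction (Wald test, assumed two-sided 5%, SE = √Σ 1/[n p(1−p)] over the four cells):
- 900 samples, equal HBS strata (600 at ≤65%, 300 at >65%): SE 0.32, power about 41%.
- 3,357 followed-up couples (section 13.4.1), 25% low HBS (Table 2: 121/478): SE 0.19, power about 84%.
- The same with 10% low HBS (section 13.5's share below 50%, used as a low bound): SE 0.27, power about 53%.

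For these low-HBS shares, the full trial is more informative on this question than the assay subset.

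**5. TUNEL.** Section 11.9.1 ranks Comet and TUNEL equal. In its Table 3, a sample with one equivalent aliquot gets cytology, TUNEL and acridine orange, but not Comet. Section 11.9 limits Comet to 450 samples. With Comet and acridine orange as the only indicators, single-aliquot samples contribute one indicator to DNAfrag while an equally ranked result goes unused.

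**The case against.** The strongest reply has four parts.

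First, section 13.7 points to Figure 6, which is not shown, and the caption is not a full list of paths (it omits HALO as a covariate for HBS). This stands as a caveat: an arm node there cannot be excluded. If there is one, the text should say so. A reader might infer that the protocol decides to pool the arms or rules out direct paths. It does neither; it names no such terms.

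Second, a reader might infer that nothing in the protocol tests the question. That is not supported. Section 13.6.1 plans interaction tests of arm by HBS and arm by sperm concentration, and links the subgroup work to the assays in section 13.7. But these tests use dichotomised factors, their listed terms contain no chromatin or DNA assay, and they are confined to generating hypotheses. That is a weak footing for a primary objective.

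Third, model detail is often left to an analysis plan. That is fair for the form of HBS or the fitting method. Here, though, the protocol itself sets out the paths and leaves out the randomised factor.

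Fourth, interactions are costly in about 900 partly assayed samples. This stands, and it is why arm interactions with every assay should not be promoted.

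**Conclusion.** The point holds for the model as described in the text. Section 13.7 names no arm or arm-by-HBS term and so, as written, cannot address whether PICSI compensates for poor sperm quality. In the illustration it returns a slope of −0.26 whether compensation is complete or absent, against interactions of 0.55 and 0. Those live birth rates are assumptions, as are the 5% test level and the low-HBS shares of 10% and 25% behind the power range of 53% to 84%.

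A reader might go further and call the model useless for the mechanistic objective. The documents do not support that: it can address HBS against chromatin integrity and HBS against live birth, and an averaged slope is still a prognostic association. Nor does Table 2 prove opposite slopes. It concerns clinical pregnancy, rests on 121 low-HBS couples, and both intervals include 1.

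No stated figure is wrong. The specification should be corrected before the mechanistic analysis is run.

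**What to change.** In section 13.7:

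1. Add arm and arm-by-HBS, with HBS continuous, to each clinical-outcome equation. Alternatively, fit a two-group model by arm with a test of equal HBS slopes.
2. Name as the analysis for the compensation objective an arm-by-HBS logistic regression in all randomised couples with HBS and outcome. Report the interaction with its 95% confidence interval and state its limited precision. This does not depend on the assay subset.
3. Add TUNEL as an indicator of DNAfrag.
4. Allow direct paths from DNAfrag, Chrom and HALO to live birth and miscarriage, so that the section delivers what section 13.1.2.2 refers to it for.
5. Keep arm-by-assay interactions exploratory.
6. Make the text and Figure 6 agree on where allocation enters.

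Arm, HBS and TUNEL are already planned data, so the cost is specification work and a few more parameters. The drawback is modest power for the interaction, which argues for estimation with an interval rather than reliance on a significance test.
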